8.1.3.8. Visits 8 & 9: Post-Lung Transplant (day 84 ±7, day 112 ±14)

Visit #8 should occur 12 weeks (84 ±7) after the subject's lung transplant and will coincide with the subject's regularly scheduled post-transplant follow-up visit. Visit #9 should occur 16 weeks (112 ±14) after the subject's lung transplant and will immediately follow the subject's regularly scheduled post-transplant follow-up visit.

Midway between these study visits, subjects will be phoned in order to ensure drug adherence, if necessary

For both visits, the staff will call the subject 1-2 days before the visit to remind subject of visit. During this phone call, the research staff will remind the subject where to go for the study visit, to take their routine and study medications as they usually would prior to the visits and, if a fibroscan is needed, inform the subject and remind him/her to not eat or drink for three hours before the study visit.

The following procedures and activities will be performed:

- Assess for Adverse Events
- Obtain medication data
- Research Phlebotomy (See Section 8.2.1 for complete list)
 - Note: Timing for HCV RNA viral load, post treatment, should, as best possible, follow the important data collection points post treatment. These are as follows:
 - Post-treatment: This should occur after the subject has completed treatment of the study drug.
 - SVR 4: This should occur ~4 weeks after the subject has completed treatment.
 - SVR 8: This should occur ~ 8 weeks after the subject has completed treatment.
 - SVR 12: This should occur ~12 weeks after the subject has completed treatment.
 - SVR 24: This should occur ~24 weeks after the subject has completed treatment.
- Fibroscan (elastography of liver) for one visit only
- Health Status Questionnaire (RAND-36) (to assess changes in health status from pre- to post-transplant)
- Pill count and verbal assessment for drug adherence
- Replenish study drug
 - Note: The staff will replenish the subject's supply of the Zepatier or Epclusa or another appropriate antiviral therapy between visits 7 & 8, if necessary. This is based on management of patients NS5A resistance variants, in any were are present. The staff will also remind the subject how to take the medication, for those subjects still on study medication.

8.1.3.9. Visit 10 Post-Lung Transplant (day 168 ±14)

Visit #10 should occur 24 weeks (168 ±14) after the subject's lung transplant and will coincide with the subject's regularly scheduled post-transplant follow-up visit.

For this visit, the staff will call the subject 1-2 days before the visit. During this phone call, the research staff will remind the subject where to go for the study visit, to take their routine and study medications as they usually would prior to the visits and if a fibroscan is needed, inform the subject and remind him/her to not eat or drink for three hours before the study visit.

The following procedures and activities must be performed:

- Assess for Adverse Events
- Research Phlebotomy (See Section 8.2.1 for complete list)
 - Note: Timing for HCV RNA viral load, post treatment, should, as best possible, follow the important data collection points post treatment. These are as follows:

- Post-treatment: This should occur after the subject has completed treatment of the study drug.
- SVR 4: This should occur ~4 weeks after the subject has completed treatment.
- SVR 8: This should occur ~ 8 weeks after the subject has completed treatment.
- SVR 12: This should occur ~12 weeks after the subject has completed treatment.
- SVR 24: This should occur ~24 weeks after the subject has completed treatment.
- Fibroscan (elastography of liver)
- Health Status Questionnaire (RAND-36) (to assess changes in health status from pre- to post-transplant)

8.1.3.10. Visit 11 Post-Lung Transplant (day 365 ±14)

Visit #10 should occur 52 weeks (365 ±14 days) after the subject's lung transplant and will coincide with the subject's regularly scheduled post-transplant follow-up visit.

For this visit, the staff will call the subject 1-2 days before the visit. During this phone call, the research staff will remind the subject where to go for the study visit, to take their routine and study medications as they usually would prior to the visits and, if a fibroscan is needed, inform the subject and remind him/her to not eat or drink for three hours before the study visit.

The following procedures and activities must be performed:

- Assess for Adverse Events
- Research Phlebotomy (See Section 8.2.1 for complete list)
- Fibroscan (elastography of liver)
- Health Status Questionnaire (RAND-36) (to assess changes in health status from pre- to post-transplant)

The Research Staff should fill out the **Study Closeout Form**. This form must be signed by the principal investigator.

8.1.3.11. Additional Visits

Additional visits will only be necessary in the case of treatment failures. If treatment failure occurs, subjects with genotype 1 or 4 infections will be treated with Zepatier and two other hepatitis C medications, Sofosbuvir (Sovaldi), and Ribavirin for an additional 12 weeks. All study and lab visits will be repeated during this secondary treatment period. NS5A resistance (RAV) testing will be checked again (a second time) prior to initiating second-line therapy.

If treatment failure occurs for patients with non-genotype 1 and non-genotype 4 infections (i.e. genotypes 2, 3, 5, or 6), the PIs will evaluate these patients for second treatment regimen that will be paid for either by the patient's insurance company or provided by HUP if the insurance company denies payment.

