--	---

	
 • Psychosocial: Profound neurocognitive impairment with absence of social support. • Active mental illness or psychosocial instability • Inadequate insurance and/or financial support for post-transplant care. • Evidence of drug, tobacco or alcohol abuse within the past six months and failure to satisfy recommended therapy/services/parameters as indicated by social work staff and/or consult team. • History of chronic non-adherence to medical recommendations and/or medications • PRA >10%. • Severe malnutrition, BMI <18 kg/m² • Major chronic disabling comorbidity (e.g. lupus, severe arthritis, neurologic diseases, previous stroke with profound residual). • Symptomatic or severe vascular disease (History of CABG, Aorta-femoral surgery)
Study design	
Open-labelled pilot clinical trial of Zepatier (MK-5172 and MK-8742/Grazoprevir + Elbasvir) or Epclusa or another appropriate antiviral treatment in up to 11 HCV-negative subjects with lung failure receiving a lung transplant from a HCV-positive donor. Eligible subjects will receive a lung transplant from a deceased-donor with detectable HCV nucleic acid, and then will receive 12 weeks of Zepatier, Epclusa, or another appropriate antiviral treatment after lung transplantation when infection with HCV is confirmed in these lung transplant recipients. For Zepatier, treatment will be complete after 12 weeks.
 
* Patients with Genotype 1a and Genotype 1 with an unknown subtype will have baseline NS5A drug resistance assay testing checked at the start of treatment, and if patients have polymorphisms at positions M28, Q30, L31, and/or Y93, treatment with Zepatier will be extended to 16 weeks, rather than 12 weeks, and renally-adjusted Ribavirin at the clinician's discretion will be initiated, and continued for the remainder of therapy (until the 16 week mark). Such a strategy will provide optimal treatment, without delaying therapy prior to receipt of results of NS5A drug resistant testing.

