7 CHAPTER 4: TREATMENTS

7.1. Zepatier (grazoprevir and elbasvir) for lung recipients with HCV genotype 1 or genotype 4 infection

Zepatier tablets will be provided by Merck as part of this investigator-initiated protocol funded by Merck. Open-label Zepatier (grazoprevir 100 mg and elbasvir 50 mg) will be administered once daily by mouth for 12 weeks. An exception to the 12 week course of treatment will be if patients have polymorphisms at positions M28, Q30, L31, and/or Y93 as determined by the Hepatitis C Viral RNA Genotype 1 NS5a Drug Resistance test. In this case, treatment with Zepatier will be extended to 16 weeks and renally-adjusted Ribavirin will be initiated at the clinician's discretion, and continued for the remainder of therapy (until the 16 week mark). Such a strategy will provide optimal treatment, without delaying therapy prior to receipt of results of NS5A drug resistant testing. Grazoprevir (GZR) / elbasvir (EBR) is a fixed-dose combination tablet without ribavirin.

GZR is an HCV ns3/4a inhibitor while EBR is an HCV NS5A inhibitor. Both are direct-acting antivirals, which together form an effective therapy for HCV virus and reduce the likelihood and effects of long-term liver-related HCV complications. GZR/EBR exhibits broad in vitro activity against most HCV genotypes and in vitro activity against many clinically relevant resistance-associated variants (RAVs).

Zepatier (GZR/EBR) has been evaluated globally in multiple phase I, II, and III trials to treat HCV. Randomized, placebo-controlled trials have been completed and led to obtain FDA approval for Zepatier as a treatment for genotype 1 and 4 HCV. As of July 1, 2015, a diverse population of over 1000 HCV patients has been exposed to Zepatier either as a single agent or in combination with ribavirin or sofosbuvir in phase I/II/III studies. Zepatier has been generally well tolerated at doses of 50-100 mg GZR and 50 mg EBR orally once daily. It has been comparably effective across all subgroups it has been tested in, including non-cirrhotic and/or treatment-naïve subjects.

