7.1.2. Administration of Zepatier

Merck & Co will manufacture, package, and label Zepatier drug. There will be one bottle per subject containing a 28-day supply (28 capsules) of 100/50 mg Zepatier tablets. Daily dose will be one tablet.

The Investigational Drug Services (IDS) pharmacy, directed by [name], will only be required to store and distribute Zepatier. Sofosbuvir and Ribavirin will be purchased and sourced locally. Both of these medications will be purchased and stored by the IDS pharmacy at Penn. Ribavirin will be generic and the manufacturer will vary depending on monthly price fluctuations.

Zepatier will be picked up from the investigational drug services (IDS) pharmacy by the research staff at 28-day intervals. The study staff will deliver the medication to the subjects at their study visits (patients expected to be at home by the time that HCV therapy is initiated and patients will be given medication at their scheduled post-transplant/study visit). Treatment with the study drug will begin within 4 weeks post-transplant. If hepatitis C is not cured after a subject has received Zepatier, he or she will be treated with a second regimen that includes Zepatier plus Sovaldi (Sofosbuvir) and Ribavirin. Any patient (male or female) receiving ribavirin as part of the first- or second-line regimen will be required to use two methods of birth control while on Ribavirin therapy, with continuing two forms of birth control for up to 6 months after the last dose of the study drug.

If patients have baseline NS5A drug resistance assay testing that demonstrates polymorphisms at positions M28, Q30, L31, and/or Y93, treatment with Zepatier will be extended to 16 weeks, rather than 12 weeks, and renally-adjusted Ribavirin at the clinician's discretion will be initiated, and continued for the remainder of therapy (until the 16 week mark). Such a strategy will provide optimal treatment, without delaying therapy prior to receipt of results of NS5A drug resistant testing.

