12.9. Subject Withdrawal

A subject has the right to withdraw from the study entirely at any time for any reason without prejudice to future medical care by the investigator or other physician. The investigator also has the right to withdraw subjects from the study in the event of concurrent illness, AEs, or other reasons deemed to be in the subject's best interest.

Subjects **must be withdrawn** from the trial (treatment and procedures) for the following reasons:

- Subject withdraws consent for study treatment and study procedures. A subject must be removed from the trial at his/her own request or at the request of his/her legally acceptable representative. At any time during the trial and without giving reasons, a subject may decline to participate further. The subject will not suffer any disadvantage as a result.

- Subject becomes pregnant while undergoing treatment with Zepatier—therapy will be stopped as there are no human safety data of Zepatier during pregnancy. There are no adequate and well-controlled studies with Zepatier in pregnant women. No effects on embryo-fetal development were observed in rats or rabbits at grazoprevir or elbasvir exposures higher than exposures in humans at the recommended clinical dose. Because animal reproduction studies are not always predictive of human response, Zepatier should be used during pregnancy only if the potential benefit justifies the potential risk to the fetus. Because the transmission rates of HCV from mother to fetus are very small, and HCV can be treated after pregnancy and delivery, therapy will not be continued during pregnancy. Patients will continue with the regularly scheduled study visits, but will not be eligible to receive continued Zepatier therapy.
- Zepatier is no longer produced by the company, or if a decision is made to stop the study patients will not receive study drug, but will continue with study visits as scheduled.
- Subject becomes pregnant while undergoing treatment with Epclusa—therapy will be stopped.
- Epclusa is no longer produced by the manufacturer, or if a decision is made to stop the study patients will not receive study drug, but will continue with study visits as scheduled.

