12.11.3. Risk of NS5a Drug Resistance Test Failure

The potential risks of the NS5a resistance testing are false negative and false positive test results. The risk of a false negative test result would be if the test does not report any one of the four pertinent polymorphisms, even though they are present (the presence of which would be rare). In this case, the patient would receive only 12 weeks of Zepatier (rather than 16 weeks of Zepatier + renal-dosed Ribavirin), and potentially fail first-line therapy, requiring second-line therapy.

A false positive result is less likely to happen than a false negative result. The risk of a false positive test result would be if the test reports a polymorphism when the subject does not have one. Hence, the subject would be exposed to Zepatier for 4 weeks longer than needed as well as Ribavirin, and potentially experiencing the products' side effects.

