12.11.4. Risk of Study Drugs

Zepatier

In subjects receiving Zepatier for 12 weeks, the most commonly reported adverse reactions of all intensity (greater than or equal to 5% in placebo-controlled trials) were fatigue, headache, and nausea. In subjects receiving Zepatier with ribavirin for 16 weeks, the most commonly reported adverse reactions of moderate or severe intensity (greater than or equal to 5%) were anemia and headache.¹⁶⁻¹⁸ The greatest risk is failure to achieve SVR12 after treatment with Zepatier, leading to chronic HCV.

There is a risk of fetal harm and birth defects should any woman taking Zepatier become pregnant while on the drug.¹⁶⁻¹⁸ Due to the age of the participants, this is a small risk, as all will be over 40 and unlikely to become pregnant. However, to mitigate this risk, all pre-menopausal women with a uterus will be screened for pregnancy before enrollment and instructed to use a highly effective form of birth control (e.g. abstinence, intrauterine device, etc.). Highly effective forms of birth control will be defined by the Mycophenolate Risk Evaluation and Mitigation Strategy (REMS), a standard protocol used for post-transplant patients at Penn being treated with Mycophenolate.

Sovaldi (Sofosbuvir)

The most common adverse events (incidence greater than or equal to 20%, all grades) observed with Sovaldi in combination with ribavirin were fatigue and headache. The most common adverse events observed with Sovaldi in combination with peginterferon alfa and ribavirin were fatigue, headache, nausea, insomnia and anemia.¹⁹

Ribavirin

The hemolytic anemia associated with ribavirin therapy may result in worsening of cardiac disease that has led to fatal and nonfatal myocardial infarctions. Significant teratogenic and embryocidal effects have been demonstrated in all animal species exposed to ribavirin. Therefore, ribavirin therapy is contraindicated in women who are pregnant and in the male partners of women who are pregnant.²⁰

Epclusa

The most common adverse reactions (incidence greater than or equal to 10%, all grades) observed with treatment with Epclusa for 12 weeks are headache and fatigue. The most common adverse reactions (incidence greater than or equal to 10%, all grades) observed with treatment with Epclusa and ribavirin for 12 weeks in patients with decompensated cirrhosis are fatigue, anemia, nausea, headache, insomnia and diarrhea.

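### Ribavirin rescue is written without exception, but no rule on giving or stopping it takes up the protocol's own contraindication for men with a pregnant partner

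*Combined protocol and SAP*

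**What the plan says.** **Rescue.** Section 8.1.3.11 (Additional Visits) says that on treatment failure "subjects with genotype 1 or 4 infections will be treated with Zepatier and two other hepatitis C medications, Sofosbuvir (Sovaldi), and Ribavirin". Section 7.1.2 names the same second regimen for a subject not cured by Zepatier. Section 7.1.5 repeats it and makes the ribavirin dose, but not whether it is given, depend on creatinine clearance. For genotypes 2, 3, 5 and 6, section 8.1.3.11 leaves the second regimen to the investigators.

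**Contraindication.** Section 12.11.4 (Risk of Study Drugs) states that "ribavirin therapy is contraindicated in women who are pregnant and in the male partners of women who are pregnant".

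**Pregnancy rules.** Section 6.2.2 excludes pregnant or nursing women. Section 8.1.2 tests women of childbearing potential. Section 12.9 requires withdrawal when "Subject becomes pregnant while undergoing treatment with Zepatier", with a parallel line for Epclusa.

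**Contraception.** Sections 7.1.2 and 8.1.3.3.1 require any patient on ribavirin, male or female, to use two methods during treatment, with "continuing two forms of birth control for up to 6 months after the last dose of the study drug". Section 6.2.1 separately requires a barrier method or abstinence after transplant for both sexes.

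**First line with NS5A polymorphisms.** Section 7.1 says that "renally-adjusted Ribavirin will be initiated at the clinician's discretion, and continued for the remainder of therapy". The Synopsis and sections 7.1.2 and 8.1.3.3.1 say much the same with a different word order. Section 12.11.3 describes the consequence of a false-negative test as 12 weeks of Zepatier, "rather than 16 weeks of Zepatier + renal-dosed Ribavirin".

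**The concern.** The rescue text tells the site to give ribavirin to every genotype 1 or 4 failure. The risk text of the same protocol names a group in whom it is contraindicated. A reader would expect an eligibility, screening, dispensing or stopping rule to connect the two. For pregnant subjects one does; for men with a pregnant partner, none visible does. A site that follows 7.1.5 and 8.1.3.11 as written could give the drug in a situation that 12.11.4 warns against, and 12.11.4 itself reports teratogenic and embryocidal effects in animals.

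The design does not make the situation implausible. Section 12.11.4 plays down pregnancy among women on Zepatier because all participants will be over 40. Section 6.2.1, however, admits subjects from age 18, and section 4.1 points to cystic fibrosis patients as among the youngest recipients.

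For the analysis, the stake is interpretability. Section 12.11.4 lists anemia among the commonest reactions to Zepatier with ribavirin, but the toxicity summaries in sections 10.3 and 10.6 and the SVR calculation in the Synopsis do not show who received ribavirin.

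**Working it through.** The main check is textual: does any operative rule reach a male subject whose partner is pregnant?

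| Rule | Section | Whom or what it covers | Reaches the pregnant-partner case? |
|---|---|---|---|
| Rescue regimen | 7.1.2, 7.1.5, 8.1.3.11 | Zepatier failures (8.1.3.11: genotype 1 or 4) | No exception; only the dose varies, with renal function |
| Exclusion | 6.2.2 | Subject's own pregnancy or nursing | No |
| Screening test | 8.1.2 | Women of childbearing potential | No |
| Pregnancy stopping rules | 12.9 | Subject's own pregnancy | No |
| Two methods on ribavirin | 7.1.2, 8.1.3.3.1 | Men and women; aims to prevent conception | Not if the partner is already pregnant; no instruction if she becomes pregnant |
| Barrier or abstinence | 6.2.1 | Men and women; stated reason is HCV transmission | Not named |
| Safety judgment at treatment start | 8.1.3.3 | Patient's overall condition | Not named |
| General withdrawal grounds | 12.9 | Concurrent illness, AEs, the subject's best interest, other significant risk | Not named |

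The first half of the contraindication (pregnant women) is therefore covered by 6.2.2, 8.1.2 and 12.9. The second half appears only in 12.11.4.

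**Contraception period.** The post-treatment wording, "continuing two forms of birth control for up to 6 months after the last dose of the study drug", bounds the period from above. It gives no shortest acceptable period.

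**First-line ribavirin.** Section 7.1 attaches the discretion to starting the drug: "renally-adjusted Ribavirin will be initiated at the clinician's discretion". In the Synopsis and in 7.1.2 and 8.1.3.3.1 the phrase follows the drug name, so it could be read as qualifying the renal adjustment. Section 12.11.3 mentions no discretion: it names ribavirin as part of the 16-week regimen, and it says a false-positive subject would be exposed to it.

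**How many subjects could reach rescue.** The plan gives no figure, so this is an illustration. Inputs: 11 treated subjects (Abstract) and a Zepatier success rate of 94-100% (section 7.1). Assumptions: all 11 have genotype 1 or 4, outcomes are independent, and that rate carries over to this setting.

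- Expected failures: 11 × (1 − 1.00) = 0 to 11 × (1 − 0.94) = 0.66.
- Chance of at least one failure: 1 − 1.00^11 = 0 to 1 − 0.94^11 = 1 − 0.506 = 0.494, about 49%.

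The documents give no figure for how many male subjects would have a pregnant partner, so the calculation stops there. A lower success rate after transplant would raise both figures.

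**The case against.** The strongest reply is that the contraindication stands in the same protocol, so investigators have been told, and no sensible clinician would read 7.1.5 in isolation. Visit 1 (8.1.3.3) requires a judgment that starting treatment is safe, and since visits are repeated in rescue, that judgment arguably applies again. Section 12.9 allows withdrawal on broad grounds. Both sexes must use contraception. The consent form and case report forms are not among the documents and may ask about partners. All this lowers the practical risk. It does not close the gap: the judgment and withdrawal clauses look mainly to the subject's own condition or interest, contraception does not help once the partner is pregnant, and the operative text still says the drug will be given.

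Several stronger readings are tempting but not supported:

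- *Section 12.9 stops treatment only for the subject's pregnancy.* It lists other grounds, including any significant risk in the investigators' judgment.
- *The contraception rule is met by stopping the day after the last dose.* The text speaks of continuing two methods, and the barrier-or-abstinence criterion in 6.2.1 has no stated end.
- *First-line discretion contradicts mandatory rescue.* These are different settings and may have different rules.
- *Section 12.11.3 makes ribavirin compulsory for every NS5A-positive subject.* It is a risk narrative that can be read as shorthand; the treatment sections, which govern, all mention discretion.
- *SVR has no defined treatment.* The Synopsis deliberately pools regimens, with no control and no planned comparison by regimen. The weight of one subject among 11 applies to any issue and does not measure an effect of this one.

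**Conclusion.** The point holds as a conflict within the protocol that bears on safety. Rescue ribavirin for genotype 1 or 4 failures is unconditional in 7.1.2, 7.1.5 and 8.1.3.11, while 12.11.4 states a contraindication that no visible giving, exclusion, screening or stopping rule takes up for men with a pregnant partner. The open-ended contraception period compounds it. The first-line mismatch with 12.11.3 is minor.

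Few subjects would be affected. On the protocol's own success rates, fewer than one of 11 would be expected to need rescue, and only some of those could be men with a pregnant partner. No bias in the SVR rate is shown. The conclusion rests on the visible text, on reading the rescue sentences as they stand, and on no unseen form supplying the missing link. It takes no position on which clinical rule is right. The change is worth making because a literal reading could expose a pregnancy to a drug the protocol warns about, and the correction is cheap.

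**What to change.** 1. Reconcile sections 7.1.2, 7.1.5, 8.1.3.11 and 12.9 with the contraindication stated in 12.11.4, so that the giving and stopping text and the risk text agree. The investigators set the clinical rule.
2. Restate the post-ribavirin contraception period in 7.1.2 and 8.1.3.3.1 so that the required length is unambiguous. The investigators set the length.
3. Align 12.11.3 with the Synopsis and sections 7.1, 7.1.2 and 8.1.3.3.1 on whether ribavirin is discretionary in first-line NS5A-positive treatment, using one word order throughout so that it is clear what the discretion covers.
4. Record for each subject whether ribavirin was given, and in which course, and list it beside SVR and adverse events. Keep this descriptive: with 11 subjects and polymorphisms that 12.11.3 calls rare, a ribavirin group may hold no one or one person.

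The cost is wording in one amendment and one extra listing. Medication data are already collected at the on-treatment visits, so little new data collection is needed.
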